4.2. Eligibility Criteria

The study will **include** dyads of parents and infants who meet the following criteria:

1. Parent can provide electronic signed and dated informed consent form.
1. Parent is willing and able to comply with all study procedures for the duration of the study.
2. Parent is a primary caretaker of an infant 0 to 2 months of age.
3. Parent is 18 years of age or older at time of consent.

4. Parent can speak, read, and write in English or Spanish.
5. Parent has a valid email address or phone that can receive text messages.
6. Parent has reliable access to the internet.
7. Infant is a patient at a participating Meta-LARC clinic site at the time of consent.

The study will **exclude** any dyad who meets any of the following criteria from participation:

8. Infant was born at less than 25 weeks gestational age.
9. Infant has established eczema as diagnosed by the primary healthcare provider at clinic site of enrollment per parent report.
10. Infant has known adverse reaction to petrolatum-based emollients.
11. Infant has an immunodeficiency genetic syndrome such as Wiskott-Aldrich Syndrome or Severe Combined Immunodeficiency Syndrome.
12. Infant has extremely low birth weight (less than 1000g or 2.2 lbs at birth).
13. Infant has a sibling enrolled in the study.
14. Parent is unwilling or unable to comply with study procedures.

4.3. Withdrawal and Follow-Up

This study has nine participant contacts, of which three (baseline, 12 months, and 24 months) are long-form questionnaires and six (at 3, 6, 9, 15, 18, and 21 months) are short responses. At each time point, we will tabulate three categories:

- Responses, including partial responses
- Missed contacts, meaning that a later response exists
- Withdrawals and losses to follow-up, where participants either inform the research team that they will not participate further, are considered lost to follow-up meaning there is no documentation in the electronic medical record and they have no 2-year visit data available given appropriate time windows, or cannot be contacted and no later contacts exist

When participants withdraw, they may give permission to include them in the final chart review to ascertain AD diagnoses. These participants would lack follow-up survey data but be included in the final analysis of provider-diagnosed AD. The general CONSORT diagram to be populated with screening and inclusion numbers for the ITT population in the final analysis is included as Figure 2.

Within each arm, we will calculate the percentage of randomized participants at each step for each of those categories. An outline of this tabulation is provided as Figure 3.

As described in our approach to missing data in the primary analysis, we will compare loss to follow up in the intervention versus control arms with an indicator of missingness at each time point. We will test for a study arm x time interaction in a population-averaged model with missingness as a binary dependent variable. These findings will inform our approach to imputing missing observations, including outcomes.

4.4. Descriptive Statistics

We will tabulate variables, including baseline characteristics, as detailed in Table 1.

5. Analysis

5.1. Statistical Hypotheses and Outcome Definitions

1. Our primary hypothesis is that the intervention will result in significantly **lower cumulative incidence of provider-diagnosed AD by age 24 months**.

After two years of follow-up, we will calculate the proportions of children diagnosed with AD by trained primary care providers in the intervention and control arms. Clinicians will be trained in pediatric AD standard diagnosis criteria.⁴ As our primary analysis, we will test the hypothesis that the ratio of the intervention:control proportions, a relative risk (RR) measure, is significantly smaller than 1 with a two-sided test: **RR ≠ 1 vs RR= 1**. This analysis will be conducted in an intention-to-treat (ITT) analysis dataset of all randomized participants with multiple imputation for missing outcomes.

Provider-diagnosed AD, the current gold standard, will be recorded during chart abstraction and referred to as **GS-AD**. The case report form (CRF) includes a question:

Was there a diagnosis of AD (includes eczema, atopic eczema, atopic dermatitis, and neurodermatitis)? with forced choice responses:

- 1, Yes
- 0, No / No documentation
- 2, Not sure / Possible - AD diagnosis is not confirmed

The CRF further elaborates:

To check "Yes", there must be an official diagnosis from a provider. If a provider is considering eczema as a possibility, or if a parent thinks the child has eczema, mark "Not Sure/Possible" and provide verbatim description from the medical record. Choose "Not sure/Possible" if there is some evidence of eczema but no official diagnosis.

All "not sure/possible" records and their explanatory notes will be reviewed by the principal investigator or dermatology physician co-investigators under blinding before the dataset is locked for analysis. Fields describing the presence and date of onset of similar or comorbid conditions-- such as candida of the skin, impetigo, and molluscum--are part of this record. Parent responses to the Childhood Eczema Questionnaire^{5,6} (CEQ) (see item 2c below) will also be available for review during this determination.

After this review, any child with a "Yes" response or adjudicated as probable AD by physician reviewers will be considered to have AD and the outcome variable will be set to equal 1. "No" and "Not sure" responses adjudicated as not probable AD will be considered not AD and the outcome will be set to 0.

We will test additional secondary hypotheses comparing the intervention arm to controls with two-sided inference tests. In all of the items below, "I don't know" responses will be treated as missing:

2. Lower cumulative incidence of AD at 24 months by alternative diagnosis definitions, namely:
 - a) **Parent report (PR-AD)** of provider diagnosis⁷, as a yes response to the following at any time during follow-up:

Over the past 12 months, has a healthcare provider said your child has eczema or atopic dermatitis?
 - b) **Diagnosis by the UK Working Party criteria⁸ (UK-AD)** at any time during follow-up, defined as a yes response to dry skin and a rash that causes itching, i.e.:

Does your child have, or has your child had, a red rash or eczema which can come and go?

Has this red rash or eczema ever caused any itching, scratching, or rubbing? (Note: Even a small amount counts)

Along with responses as follows (note that responses can be given at different data collection time points):

- [at least one selected] Select all of the areas where the red rash or eczema has been in the past year:
 - Cheeks
 - Around the eyes, ears, scalp, forehead, or neck
 - Folds (creases) of elbows or behind the knees
 - Wrist or ankle
 - Outer arms/ legs
 - Trunk
- [at least one yes] Has at least one of your baby's blood-related PARENTS, BROTHERS OR SISTERS ever been diagnosed with asthma, or hay fever (seasonal allergies)?
 - Has your child ever been diagnosed with asthma by a healthcare provider?
 - Has your child ever been diagnosed with hay fever or springtime allergies by a healthcare provider?
 - Has your child ever been diagnosed with a food allergy by a health care provider?
- [Yes] Does your child have dry skin?

Note that the published version includes food allergy in first degree relative, which is not collected in this study.

c) Diagnosis by validated multi-item **Childhood Eczema Questionnaire (CEQ-AD)** completed by parent^{5,6}, if yes responses to all of the following three questions at any time during follow-up:

Does your child have, or has your child had, a red rash or eczema which can come and go?

Has this red rash or eczema ever caused any itching, scratching, or rubbing? (Note: Even a small amount counts)

Has this red rash/eczema affected any of the following areas during the last week: around the eyes, ears, scalp, cheeks, forehead, neck, trunk, folds of the elbows/behind the knees, wrist or ankle, outer arms/legs?

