2.2 Study Outcome Measures

2.2.1 Primary Outcome

The primary outcome will be an AD diagnosis made by the infant's primary healthcare provider by 27 months of age (cumulative incidence). A diagnosis will be recorded in the health record for each infant and these data will be extracted by PBRN research coordinators. Diagnosis guidelines and documentation will be introduced at an initial training session and provider compliance with this protocol will be monitored and reinforced by PBRN research coordinators. Any diagnosis of AD made by the trained provider during the first 27 months of life will be considered as having developed AD (i.e., cumulative incidence). Clinicians will be trained to use the American Academy of Dermatology (AAD) Consensus Criteria for diagnosing pediatric AD.³⁷ These criteria are a distillation of the original Hanifin-Rajka criteria with minor enhancements made by pediatric dermatologists to facilitate diagnosis in the very young. The recently-published AAD guidelines of care for AD recommend these criteria for the diagnosis of AD in the clinical setting.³⁸ The statistical analysis plan contains the full set of primary and secondary outcomes.

Table 1: AAD Consensus Criteria for diagnosing pediatric AD.

| ESSENTIAL FEATURES |
|---|
| Must be present: |
| -Pruritus |
| -Eczema (acute, subacute, chronic) |
| -Typical morphology and age-specific patterns* |
| -Chronic or relapsing history |
| *Patterns include: |
| 1. Facial, neck, and extensor involvement in infants and children |
| 2. Current or previous flexural lesions in any age group |
| 3. Sparing of the groin and axillary regions |
| IMPORTANT FEATURES |
| Seen in most cases, adding support to the diagnosis: |
| -Early age of onset |
| -Atopy-personal and/or family history |
| -Immunoglobulin E reactivity |
| -Xerosis |

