3 STUDY DESIGN

3.1 Study Design Overview

This is a pragmatic, multi-site, randomized community-based trial that will enroll dyads of a parent or guardian (“parent”) and an infant who is up to 2 months old. Both high-risk infants (with family history of atopic disease) and average-risk infants (with no family history of atopic disease) will be eligible. Each dyad will be randomized to the intervention arm (daily emollient therapy) or the control arm (encouraged to adhere to current infant skin care guidelines without regular emollient use). Over the course of two years, 1,250 dyads will be enrolled in the trial with 625 dyads assigned to each study arm. It is anticipated that 2,500 dyads will be screened in order to reach the target enrollment.

Once randomized, dyads will participate in the study until the infant is 24 months of age (approximately two year study duration). Parents will complete a questionnaire at enrollment (prior to randomization) and follow-up annual questionnaires when the infant is 12 and 24 months old. Every three months of child’s age (e.g., age 3 months, 6 months, 9 months, etc.), parents will be contacted via e-mail or SMS text message and asked to complete a quarterly survey, have an opportunity to update their contact information, report on adherence to study arm, be given messages about daily emollient use or general infant skin care guidelines and report adverse events and serious adverse events. Finally, two weeks after enrollment into the study, dyads in both arms will receive an e-mail or text message with a brief study message for both arms, with the intervention arm getting an additional message encouraging daily emollient use.

Total study duration will last for five years, with enrollment projected to be completed at the end of study year 2 and data collection projected to be completed at the end of study year 4. After completion of the screening and enrollment, participant-specific links to subsequent questionnaires will be sent by e-mail or SMS text message. Follow-up for incomplete questionnaires, unresponsive participants, as well as for individuals that did not have a valid e-mail address or phone that could not receive text messages may receive additional contact from the Clinical Coordinating Center (CCC).

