3.3 Treatment Arms

There are two arms in the study- intervention and control. Both study arms will receive text messages and e-mail links providing general skin care educational material

throughout the study. This general skin care information includes information regarding the use of gentle cleansers, bathing safety tips and managing rash. All dyads will be reminded of their treatment arm every three months via electronic survey and e-mail. Both arms will be contacted at the same frequency. There are no evidence-based guidelines for frequency of bathing. Because bathing practices vary between families considerably, only general bathing tips will be provided to both groups.

3.3.1 *Intervention Arm*

Dyads assigned to the intervention arm will receive a study-approved emollient of their choice by mail at regular intervals throughout the study and instructed to use the emollient once-daily over the entire body. Parents may avoid the scalp, if needed. Quarterly reminders will be sent during the course of the study instructing parents on the daily use of the study emollient. In addition, the intervention group will receive general infant skin care information identical to the control group.

3.3.2 *Control Arm*

Dyads assigned to the control arm will be instructed to refrain from routine emollient use and only use emollients on an “as needed” basis if their baby develops dry skin. Like the intervention group, dyads in the control arm will also receive general infant skin care guidelines. Information in the control educational materials will include general infant skin care recommendations, such as bathing and rashes. The information in educational materials will be current standard of care for the topics included.

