5.2. Definitions for Subpopulation Analyses

In **exploratory analyses** we will investigate potential differences in treatment effect in subgroups with known or hypothesized risk or protective associations with AD using the approach given in section 5.5 below. The subgroups to be investigated are:

1. **Family history of atopy in a first-degree relative**, associated with approximately doubled risk of AD¹³⁻¹⁶ and expected in 40 to 60 percent of the population, as found in our planning grant and suggested in other studies of IgE sensitization in the population¹⁷. This is one of

our stratification variables for randomization. If the elevated risk in this population is explained by filaggrin gene mutations affecting the skin barrier, then emollient use should be most protective in babies with a family history of atopy; this would point to recommending daily emollient use only in this high-risk population.

We will treat this as a binary variable (*yes* vs *no/don't know*) to the following question:

Has at least one of your baby's blood-related PARENTS, BROTHERS OR SISTERS ever been diagnosed with asthma, eczema (atopic dermatitis) or hay fever (seasonal allergies)?

2. **Dry climate**, which we will measure using the average relative humidity over a year for the clinic's locality in records from the National Climate Data Center and Weather Service. More detailed methods will be developed, following the general approach in previous work, where a protective effect of RR 0.8 was observed in the highest humidity areas¹⁸. If emollient prevents AD by preserving the skin barrier, then the treatment effect should be greatest in low-humidity areas.
3. **Having pets or regular contact with farm animals at baseline**. Meta-analysis has found a protective effect for exposure to dogs (RR 0.72) and pets overall (RR 0.75), with more equivocal evidence for exposure to cats (RR 0.94)¹⁹. We expect about 30% of participants to own cats and 40% to own dogs based on large national pet ownership surveys. This analysis will be conducted in two steps. The first step will use a set of indicator variables for the following yes/no questions, and the second will use an overall binary variable for any regular contact with animals:

Does your baby have regular (at least weekly) contact with farm animals?

Does your family own one or more dogs?

Does your family own one or more cats?

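### The UK Working Party AD endpoint requires reported dry skin, which the emollient acts on directly, so it can favour the intervention without any AD being prevented

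*SAP*

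**What the plan says.** SAP 5.1 item 2b opens by describing UK-AD as "defined as a yes response to dry skin and a rash that causes itching". It then requires at least one affected body area in the past year, at least one yes in a list of atopic conditions, and a yes to "Does your child have dry skin". No rule lets a child qualify on only some of these. The atopy list accepts asthma or hay fever in a parent or sibling, or the child's own diagnosed asthma, hay fever or food allergy. UK-AD counts at any time in follow-up, and the components need not coincide ("note that responses can be given at different data collection time points"). SAP Table 4 summarises dry skin at 12 and 24 months.

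SAP 5.4 item 2c tests UK-AD in the ITT dataset with a log-binomial model. SAP 3.1 sets 0.05 for each secondary outcome, and 3.2 makes no multiplicity adjustment.

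Protocol 5.1 says petrolatum-based emollients improve hydration. One arm applies emollient daily. Under Protocol 3.3.2 controls use it only on an as-needed "basis if their baby develops dry skin". The diagnostic criteria in Protocol Table 1 list xerosis and atopy among features "Seen in most cases, adding support to the diagnosis", not among the essential ones.

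On the population, Protocol 3.1 states that "average-risk infants (with no family history of atopic disease) will be eligible" alongside high-risk infants. SAP 5.2 gives family history of atopy as "expected in 40 to 60 percent of the population", with roughly doubled AD risk.

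**The concern.** One compulsory component of UK-AD is a skin state that the intervention changes by itself. Take two children with the same itchy rash, sites and atopic history. If the one given daily emollient is never reported as dry, that child is not a UK-AD case and the other is. Classification then depends on arm, and the expected direction favours emollient. Item 2b does not discuss this.

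UK-AD is offered as an alternative definition of cumulative AD incidence, so a significant result would naturally be read as support for prevention. It is also a candidate predictor of missingness, and hence for the imputation model (SAP 5.9), and could be one of the definitions in the planned multivariate or latent-variable analysis (SAP 5.4).

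A second, separate matter is coverage. A child with no parent or sibling with asthma or hay fever can meet UK-AD only through the child's own allergic diagnosis by about age 2. That also covers children whose only family history is eczema, because the UK-AD family item omits eczema while the stratification question includes it. This costs events and representativeness. It does not favour an arm.

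**Working it through.** **The plan's own figure.** SAP 2.3: 24% v 16.8%, two-sided 0.05, 80% power. With pooled p = 0.204:

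n = [1.960·√(2·0.204·0.796) + 0.842·√(0.24·0.76 + 0.168·0.832)]² / 0.072² = 490.5, so 491 per arm and 982 in total, as stated. Of 1,250 enrolled, 20% loss leaves 1,000, or 500 per arm. The documents give no incidence or power for UK-AD.

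**AD risk by family history.** With prevalence f and doubled risk, the risk without family history is r = 0.24/(1 + f). The share of AD cases without family history is (1 − f)·r/0.24 = (1 − f)/(1 + f): 0.43, 0.33 and 0.25 for f = 0.4, 0.5 and 0.6. At f = 0.5 (SAP Table 1), AD risk is 32% with and 16% without family history, and AD cases with family history are 0.5 × 0.32 = 16% of all infants.

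**Dry-skin path with no effect on AD.** UK-AD RR = P(dry | case, intervention) / P(dry | case, control). For the error rate I take UK-AD risk = 0.16 × dry-skin share. This assumes that every family-history case meets the other conditions and that no other child qualifies. The chance of a significant result favouring emollient is Φ[(d − 1.96·se₀)/se₁] at 500 per arm, with d the risk difference, se₀ the pooled and se₁ the unpooled standard error. For 80% v 60%: risks 0.128 and 0.096, d = 0.032, se₀ = 0.01995, se₁ = 0.01992, giving Φ(−0.356) = 0.36.

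Those rates may describe either a yes at any time or a yes on each questionnaire. In the second case, with two independent answers, the ever-yes rate is 1 − (1 − p)².

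| Assumed dry-skin rate among cases, control v intervention | RR, rates as ever-yes | Chance of false benefit | Ever-yes from two independent answers | RR | Chance of false benefit |
|---|---|---|---|---|---|
| 90% v 80% | 0.89 | 11% | 99% v 96% | 0.97 | 4% |
| 80% v 60% | 0.75 | 36% | 96% v 84% | 0.88 | 14% |
| 70% v 50% | 0.71 | 40% | 91% v 75% | 0.82 | 22% |

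The nominal rate in that direction is 0.05/2 = 2.5%. Two answers from the same child are likely to be positively correlated, which puts the truth between the two halves of the table for a given gap. A smaller gap gives less: 80% v 75% as ever-yes gives RR 0.94 and about 6%. With the dry-skin condition removed, the RR in this model returns to 1.00 and the rate to 2.5%.

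**Atopy condition.** Suppose a fraction q of AD cases without family history have their own qualifying diagnosis. At f = 0.5 their share of UK-AD cases is 0.08q/(0.16 + 0.08q), where 0.08 = 0.5 × 0.16; the dry-skin share cancels. For assumed q of 5% to 30% this is 2% to 13%, against 33% of all AD cases. The documents give no value for q.

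**The case against.** The strongest reply is that the effect may be small. UK-AD counts at any time and accepts answers from different contacts, so one dry-skin yes is enough. Among children with a rash, emollient use is likely to converge between arms: controls may use it for dry skin, clinicians keep treating skin disease (Protocol 4.5), and SAP 5.7 accepts that use after diagnosis reflects treatment. Protocol 1.5.1 also reports that over 70% of parents already moisturise daily. All of this stands. It shrinks the bias but gives no reason for it to vanish or reverse.

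It is also fair that PR-AD and CEQ-AD carry neither condition, and that SAP Table 4 already tabulates dry skin by arm. That tabulation covers all ITT children, not those with an itchy rash, so it would show an imbalance without showing its effect on UK-AD.

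Three stronger readings are tempting and not supported.

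- A reader might infer that the atopy condition biases the comparison. It applies alike to both arms.
- A reader might infer that average-risk infants can hardly ever qualify. That needs rates of their own asthma, hay fever or food allergy, which the documents do not give.
- A reader might infer from Protocol Table 1 that item 2b is wrong and should become itchy rash plus any site. An alternative definition may differ from the primary criteria, the cited instrument cannot be checked here, and that replacement would nearly duplicate CEQ-AD, differing mainly in past-year v last-week recall of site.

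**Conclusion.** UK-AD as written can favour emollient with no effect on AD, because a compulsory component is itself a target of the intervention. The direction follows from the text; the size does not. Under the assumed dry-skin rates the spurious RR runs from 0.89 to 0.71 (false benefit about 11% to 40%) if they are ever-yes rates, and from 0.97 to 0.82 (about 4% to 22%) if they are independent per-questionnaire rates. These rest on my dry-skin rates, 50% family-history prevalence, 500 per arm, and no average-risk child qualifying.

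The atopy condition is a coverage limit: UK-AD under-represents infants who supply 25% to 43% of expected AD cases on the SAP's inputs.

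A reader might go on to doubt the trial's main result. The documents do not support that: the primary GS-AD definition requires neither item, and SAP 5.4 lists UK-AD as one of several secondary or sensitivity definitions.

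**What to change.** Keep the stated UK-AD definition. Before unblinding, amend SAP 5.1 item 2b and 5.4 item 2c as follows.

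1. Add a second version with the dry-skin condition removed and the itch, site and atopy conditions kept, so that it does not duplicate CEQ-AD.
2. Report both versions side by side, overall and by family-history stratum.
3. Report dry skin by arm among children with an itchy rash. This is descriptive, since the subgroup is defined after randomisation.
4. State that a UK-AD benefit that disappears when the dry-skin item is dropped is not evidence of AD prevention.

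The cost is one derived variable from items already collected and a few lines of SAP text. The added version is less specific and departs from the cited instrument; the SAP already departs from it by not collecting food allergy in relatives.

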at 2 years independent of filaggrin genotype or family history.¹⁸ These findings were confirmed by Ohya and colleagues in a separate cohort of 118 infants in Japan.¹⁹ Once early skin inflammation is initiated, a cycle of skin barrier dysfunction and inflammation ensues. Inflammatory infiltrates and Th2 cytokines then alter the expression of several important components of the skin barrier.^{20,21} This may explain why skin barrier dysfunction can be found in patients with AD regardless of filaggrin status.²² Barrier enhancement early in life could not only correct skin barrier defects that are the direct results of a mutation in skin barrier genes, but should also correct skin barrier dysfunction resulting from harsh bathing practices or other environmental insults. In addition, emollients have anti-inflammatory effects that could suppress early sub-clinical inflammatory infiltrates that may also initiate the disease.²³ This idea is supported by the fact that emollients prevent flares of AD in populations not selected for filaggrin status and our pilot data shows a protective effect of emollients independent of FLG status.^{24,25}

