2.2.2 Secondary Outcomes

- Parental report of provider-diagnosed AD - This parental report of AD question has been validated previously by our group and was found to have adequate sensitivity and specificity during our trial planning activities.³⁹

- AD as diagnosed by the Children's Eczema Questionnaire (CEQ) – The CEQ is a newly developed 2-question parental questionnaire based on the U.K. Working Party criteria.⁴⁰ This instrument will be used to capture dyads not evaluated by their provider or lost to follow-up (Appendix A).
- Parental report of sleep loss of the infant reported as average parental report of days per week of disrupted sleep in their infant (1 week recall) measured at 12 and 24 months.
- Any prescription topical medication use or over-the-counter hydrocortisone usage recorded by parent or recorded from records review by research coordinator at 24 months.
- Asthma risk questions from the modified Asthma Predictive Index (mAPI) that uses family history, atopic dermatitis, sensitization history, and wheezing episodes to predict the development of asthma measured by parental report.⁴¹ This will be recorded as either high risk or low-risk at 12 and 24 months following mAPI criteria (Appendix B). Wheezing episodes will be assessed using the International Study of Asthma and Allergies in Childhood (ISAAC) questionnaire.
- Parental report of immediate food allergy symptoms – A general question regarding the development of red rash/hives, lip swelling, wheezing, abdominal pain, or vomiting that developed in the infant within two hours of eating a food.
- Parental report of a provider diagnosis of food allergy that was confirmed by prick testing or IgE blood test.
- One question global health status from the PROMIS Pediatric Global Health (PGH-7) instrument.⁴² (Appendix C)
- In infants who develop AD, a logic model in our survey instrument will ask the following parental reported outcomes in the 12- and 24-month questionnaires:
 1. Time to onset of AD as measured by parental report of eczema age of onset.
 2. Time to onset of AD as measured by provider-recorded date of first diagnosis retrieved from record review of chart by research coordinator.
 3. AD symptom severity as reported by the Patient-Oriented Eczema Measure (POEM) instrument⁴³ (Appendix D).
 4. Parent-reported global severity of eczema assessment – mild, moderate, severe

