2.6. Timing of Outcome Assessments

Endpoints are assessed briefly at 3-month intervals and in depth at 12 and 24 months of age. These include diagnosed AD, severity of symptoms, and development of potentially related conditions, such as allergies.

Table 2. Timing of assessments

Assessment	Child age	Window
Screening	≤ 2 months	0-9 weeks
Contact 1	≤ 2 months	0-9 weeks
Contact 2	3 months	± 14 days
Contact 3	6 months	± 14 days
Contact 4	9 months	± 14 days
Contact 5	12 months	-4 weeks + 12 weeks
Contact 6	15 months	± 14 days
Contact 7	18 months	± 14 days
Contact 8	21 months	± 14 days
Contact 9	24 months	-4 weeks + 12 weeks
Final Contact	24 months chart audit	Through 27 months of age

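### CEQ-AD is tested as cumulative incidence of AD to 24 months, but it needs rash in the week before the 12- or 24-month questionnaire, so it measures active disease at two points

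*SAP*

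**What the plan says.** SAP 5.1 item 2 sets the secondary hypothesis: "Lower cumulative incidence of AD at 24 months by alternative diagnosis definitions". CEQ-AD is item 2c. A child is positive "if yes responses to all of the following three questions at any time during follow-up". The first question is of the ever type: "Does your child have, or has your child had, a red rash or eczema which can come and go". The second, on itching, is also of the ever type. The third is not: "Has this red rash/eczema affected any of the following areas during the last week".

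On timing, SAP 2.6 says "Endpoints are assessed briefly at 3-month intervals and in depth at 12 and 24 months of age", and Table 3 marks the CEQ at Contact 5 (12 months) and Contact 9 (24 months) only. The quarterly contacts listed in Protocol 6.2 cover reported diagnosis, emollient use and adverse events, with no CEQ items.

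SAP 5.4 item 2d tests CEQ-AD in the ITT dataset with the same type of model as the primary outcome. Table 4 lists it as cumulative incidence at 12 and 24 months, summarised by a relative risk. The other definitions look back further: PR-AD asks about the past 12 months, and the UK-AD site item reads "Select all of the areas where the red rash or eczema has been in the past year".

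**The concern.** A cumulative-incidence label promises that any child who has had AD by 24 months is counted. CEQ-AD cannot deliver that. It sees two single weeks in about two years, and a child whose AD is quiet in both is classed with children who never had it.

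The two weeks also fall while the intervention is running. Protocol 3.3.1 has the intervention arm using emollient daily over the whole body. Protocol 3.3.2 has controls using it only as needed for dry skin. Protocol 1.2 itself argues that "emollients prevent flares of AD in populations not selected for filaggrin status". The last-week item can therefore respond to control of existing disease as well as to prevention of new disease. SAP 5.7 recognises the same distinction when it excludes emollient use reported after an AD diagnosis as probable treatment, but CEQ-AD makes no such separation.

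At stake is how a favourable CEQ-AD result is read. Under its present label it would be cited as supporting evidence that emollient reduces incidence, which is the trial's central hypothesis.

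**Working it through.** **Inputs from the documents.** Control cumulative incidence 24%, intervention 16.8% (RR 0.70), two-sided 0.05, 80% power, 491 per arm (SAP 2.3). The documents give no figure for CEQ-AD.

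**Assumed inputs.** q is the share of ever-AD children with rash in at least one index week. s is the proportional reduction of that share on daily emollient. False positives are set to zero. A two-proportion test stands in for the planned log-binomial model, so the results are indicative.

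**Formula.** With d = p1 − p2 and p̄ their mean, se0 = √(2p̄(1−p̄)/n), se1 = √((p1(1−p1)+p2(1−p2))/n), and power = Φ((d − 1.96·se0)/se1).

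**Plan's own figure.** 24% v 16.8% gives 491 per arm, 982 in total, with power 80.0%. This matches SAP 2.3.

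**Step 1: equal under-capture, true RR 0.70.** The observed rates are 0.24q and 0.168q. Their ratio is 0.70 for every q, and only power changes.

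| q | Control | Intervention | Power, 491 per arm | Total N for 80% |
|---|---|---|---|---|
| 1 | 24.0% | 16.8% | 80.0% | 982 |
| 0.9 | 21.6% | 15.1% | 74.7% | 1,120 |
| 0.75 | 18.0% | 12.6% | 65.2% | 1,394 |
| 0.6 | 14.4% | 10.1% | 54.2% | 1,806 |
| 0.5 | 12.0% | 8.4% | 46.2% | 2,218 |
| 0.4 | 9.6% | 6.7% | 37.8% | 2,836 |

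Example at q = 0.75: d = 0.054, se0 = 0.02298, se1 = 0.02291, (0.054 − 1.96 × 0.02298)/0.02291 = 0.39, and Φ = 65.2%.

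**Step 2: no prevention, activity suppressed.** Ever-AD is 24% in both arms. The observed rates are 0.24q and 0.24q(1−s), so the apparent RR is 1 − s. Two-sided rejection over q = 0.4 to 0.75:

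| s | Apparent RR | Rejection rate |
|---|---|---|
| 0 | 1.0 | 5% |
| 0.1 | 0.9 | 8–12% |
| 0.2 | 0.8 | 19–33% |
| 0.3 | 0.7 | 38–65% |

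**Step 3: the two cases cannot be told apart.** Prevention of 30% with no suppression gives 0.24q v 0.168q. No prevention with 30% suppression gives 0.24q v 0.24q × 0.7 = 0.168q. The expected CEQ-AD data are identical.

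**Step 4: the past-year site item as an alternative.** The 12- and 24-month windows run from −4 to +12 weeks (SAP Table 2). A first form at week 48 covers up to week 48. A second form at week 116 looks back to week 116 − 52 = 64. The gap is 16 weeks. Specificity also matters: with a false-positive rate f among children without AD, the observed rate is p + f(1−p). For f = 10%, 20% and 30% (assumed), a true RR of 0.70 becomes 0.79, 0.85 and 0.89.

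**The case against.** The rule counts a positive at either questionnaire, so a child positive at 12 months stays positive after remission. That stands: a reader might infer that all remitted AD is lost, but only AD inactive in both weeks is.

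A reader might also infer that CEQ-AD is biased in favour of the intervention. The documents do not establish this. Controls may use emollient for dry skin, Protocol 5.8 places no restriction on treating skin conditions, and Protocol 1.5.1 reports that over 70% of parents already moisturise daily, though mainly with watery lotions. Activity among children with AD may differ little between arms, and at s = 0 the relative risk is not distorted. The remark in Protocol 1.1 that many mild cases are outgrown gives no timing, and a chronic or relapsing course could equally put rash in an index week.

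Symptom suppression is not confined to CEQ-AD. It could delay chart or parent-reported diagnosis, and UK-AD includes a present-tense dry-skin item. This stands, but it does not make a last-week item fit a cumulative label.

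A further inference would be that the primary outcome is compromised, because Protocol 2.2.2 says of the CEQ: "This instrument will be used to capture dyads not evaluated by their provider or lost to follow-up". The SAP does not use it as a substitute. In SAP 5.9, CEQ signs of AD are one of seven variables checked for association with missingness, and an auxiliary variable need not record the outcome completely. In SAP 5.1, CEQ answers are one source available to blinded physicians reviewing uncertain charts.

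Finally, Table 4 already lists both time points, and SAP 5.4 calls these secondary or sensitivity analyses and adds a multivariate or latent-variable analysis across definitions. CEQ-AD will not be read alone, but the label still needs correcting.

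**Conclusion.** The mismatch is confirmed from the text alone: a cumulative-incidence hypothesis, a required last-week item, and two administrations. CEQ-AD measures active AD at about 12 and 24 months. It misses AD quiet in both weeks, and a lower rate in the intervention arm is not by itself evidence of fewer new cases.

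The size cannot be derived from the documents. Under equal capture the relative risk is intact, and power for the design effect is about 65% at 75% capture and 46% at 50%. The rejection rates in step 2 show what assumed suppression would do. They are not an estimate of bias in this trial. CEQ-AD is secondary, and the instrument itself is not faulted. What needs changing is its use under this label.

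**What to change.** In SAP 5.1 item 2c, 5.4 item 2d and Table 4:

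- Relabel CEQ-AD as prevalence of active (last-week) AD and report it separately at 12 and 24 months, each from that questionnaire alone.
- Take it out of the cumulative-incidence hypothesis in item 2.
- State that a difference in CEQ-AD may reflect prevention, symptom control or both, and is not evidence of reduced incidence.

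Optionally, as a labelled sensitivity analysis only, derive a variable from CEQ questions 1 and 2 plus at least one site on the past-year area item already collected for UK-AD. State that it is not the validated CEQ, is less specific, can leave up to about 16 weeks between recall windows (more if the 12-month form is missed), and still does not separate prevention from suppression. It should not replace CEQ-AD as the cumulative test.

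The CEQ may stay as an auxiliary variable in the missing-data model.

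The cost is SAP wording and a changed table row, plus one derived variable if the option is taken. No new data are needed, and SAP version 3.0 records itself as written before analysis. What is given up is one supporting test of the incidence hypothesis.
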